### **Summary of Significance, Impact, and Innovation**

For the last two decades, the conventional wisdom has underscored the importance of targeting dopamine circuits, either directly or indirectly, by using medications that act as antagonists, agonists, or mixed agonists at dopamine receptors (e.g., aripiprazole, quetiapine) or other receptor systems that may modulate dopamine function indirectly (e.g., naltrexone, ondansetron, varenicline). Given the extant body of work, the results have been somewhat disappointing, as only naltrexone eventually received FDA approval as a treatment for AUDs. Rather than targeting receptors that influence neural circuits, it may be more effective to target the molecular mechanism, at the level of transcription, which underlies changes in dopamine receptors and the function of the reward circuit (e.g., epigenetic modifications). Likewise, perturbation in immune system function is just now emerging as an important target.

Importantly, what has been largely overlooked in most research on AUDs is that there may be psychosocial interventions that exert top down control over epigenetic and inflammatory mechanisms and could be equally or more effective than medications while having fewer side effects. Although this has been largely untested in the alcohol field, there are close to a dozen studies in other patient populations to suggest that MBIs may have exactly this type of effect. If psychosocial interventions, such as MBRP, are demonstrated to be efficacious and the active ingredients can be harnessed and focused, the field will potentially see much greater success.

Thus, the significance and impact of the first aim of the proposed research stems from the simple notion that understanding how a given treatment may be effective informs efforts to increase the effectiveness of that treatment. The proposed study will serve to dismantle the effects of the mindfulness components from the relapse prevention components and test innovative and unique hypotheses about how the mindfulness components work in an AUD patient population. Specifically, the first aim will isolate the effect of Mindfulness from Relapse Prevention by comparing MBRP to RP only. Two published studies to date suggest that MBRP is more effective than RP only ([name] et al., 2014; [name] et al., 2014). However, these two studies were conducted in samples of individuals with a variety of substance use disorders, rather than AUDs specifically. Thus, the first aim is significant because it will be the first large, randomized trial to dismantle the effect of MBRP from RP in a sample of individuals with a primary diagnosis of AUD. The second aim will isolate the effects of mindfulness on key neurobiological mechanisms by determining whether MBRP influences epigenetic regulation of key genes and influences immune system function as compared to RP. The third aim will determine whether the effect of mindfulness on drinking outcomes is mediated by the effect of mindfulness on epigenetic regulation and immune system function. Because no other clinical scientists are targeting epigenetic and immune system changes in AUD treatment trials (to our knowledge), this study and this program of research are highly innovative. In addition, our vertical integration of

epigenetic regulation, immune system function including an ex-vivo LPS challenge of PBMCs, a neuroimaging assessment of changes at the neural circuit level, and clinical assessments is innovative and unique from a methodological perspective.

From a clinical perspective, identification of the molecular mechanisms that mediate the effects of mindfulness in AUD patients can then be leveraged in a variety of ways. This information may be used in future studies to test how MBIs might be refined to increase the effect of the intervention on these mechanisms. For example, does increasing the dose/practice of mindfulness increase the effects of the intervention on inflammatory pathways and/or epigenetic regulation of key genes? Would booster sessions at regular intervals after the initial 8-week training increase the effects of mindfulness practice on the immune system? Would combining MBRP with other interventions that putatively target the same mechanisms (e.g., exercise) increase the effects? All of these questions can be asked and answered once we have verified the underlying mechanisms and identified measurable biomarkers. Finally, knowledge about the mechanisms may also be used to develop an important intermediate and inexpensive test of treatment success. For example, if changes in immune system function or epigenetic regulation at 4 weeks are highly predictive of relapse after treatment, tests of immune system function or epigenetic regulation could be used to determine whether the treatment is having an effect early in the process, allowing treatment providers to alter the dose and/or treatment for non-responders. As an analogy, a primary care physician will prescribe a treatment to prevent heart disease (e.g., a statin) and then order a cholesterol test to determine if the statin is working. If not, the dose is increased or a different treatment is prescribed. In the same way, tests of immune function or epigenetic regulation may be used to check on the effect of the AUD treatment early in the process.

Due to the COVID-19 situation we are collecting remote data only and will return to our original protocol when it is safe to do so. The remote version of this study will use telehealth therapy and thus the following references have been included for BACKGROUND AND SIGNIFICANCE:

Although in-person psychotherapies have always been the norm, telehealth is increasingly becoming a more common, convenient and effective alternative. A study of evidence-based psychotherapy for PTSD and depression found that home-based telehealth is a treatment with clinical outcomes matching those of in-person clinic-based delivery systems (Acierno et al., 2016). A more recent systematic review of numerous studies looking at telemedicine's effectiveness in substance use disorders showed this method of therapy had high patient satisfaction and was an effective alternative to in-person psychotherapy (Lin, Casteel, Shigekawa, et al., 2019). Finally, a study looking at the increasing use of telemedicine versus in-person therapy for opioid use disorder revealed that patients treated via telemedicine were more likely to stay in therapy than patients treated in-person ( $n = 1590$ ; aOR = 1.27; 95% CI 1.14–1.41;  $p < 0.001$ ). At the one-year mark, telemedicine patient's retention rate was 50%, while in-person patients were at 39% retention (Eibl et al., 2017).

### **III. PRELIMINARY STUDIES**

#### **Epigenetic Mechanisms.**

To date, we have performed a number of experiments to validate our epigenetic approach and determine whether epigenetic modifications play a role in the etiology of AUDs. The results suggest that our approach is feasible and that epigenetics is involved in the etiology of AUD.

In order to validate that DRD2 methylation changes are functionally significant and that DNA methylation in peripheral tissue like blood is correlated with protein levels in the brain, we conducted a series of studies in which we sequenced bisulfite treated DNA to estimate the amount of methylation in a 655 base amplicon in the promoter region of the DRD2 that previously demonstrated an effect. These data and the data described below have been bundled into one manuscript and have been submitted for peer review. The first experiment examined the association between D2 binding potential using PET and the degree of methylation in this amplicon. To reduce Type I error, the first analysis examined the average methylation across the amplicon in relation to [C]raclopride binding (BPND) reflecting DA D2/D3 receptor availability in the nucleus accumbens. The correlation between DRD2 methylation and average of right and left accumbens BPND was  $r = 0.650$ ,  $p = 0.022$  (correlations for left and right individually were  $r = 0.55$  and  $r = 0.72$ ).

Representation of the functional relationship between the average methylation of these CpGs and striatal BPND are shown in the brain map and scatter plots in **Figure 2**.

### **DRD2 Methylation and BOLD Response to Alcohol Cues.**

BOLD response to alcohol cues in the nucleus accumbens and caudate were extracted from each individual in a previously collected data set ( $n=78$ ). Correlations between the BOLD response to alcohol cues in these structures and the average methylation of the 17 CpGs were calculated. Negative correlations were found between the average methylation of the 17 CpGs and the bilateral caudate (left:  $r = -0.273$ ,  $p = 0.027$ ; right:  $r = -0.305$ ,  $p = 0.013$ ) and nucleus accumbens (left:  $r = -0.247$ ,  $p = 0.045$ ; right:  $r = -0.241$ ,  $p = 0.052$ ).

[figure not shown]
### **DRD2 Methylation and Clinical Measures of Alcohol Dependence.**

Again using the clinical sample ( $n=78$ ), three commonly used measures of severity were negatively correlated with average methylation of the 17 DRD2 CpGs, controlling for age (AUDIT:  $r = -0.276$   $p = 0.015$ ; Alcohol Dependence Scale:  $r = -0.295$ ,  $p = 0.008$ ).

Finally, our most recent epigenome-wide analyses indicate that the dopamine transporter gene (SLC6A3) and dopamine beta hydroxylase gene (DBH) are also important epigenetic targets, and thus, we have included these additional genes.

To identify treatment implications, we also examined DRD2 methylation as a predictor of treatment outcome in a subsample of 50 individuals from a previous trial with olanzapine (Littlewood et al., 2014). Methylation in the DRD2 promoter was associated with less ability to control alcohol use

**Figure 2.** The correlation between methylation across 17 CpGs in the DRD2 promoter region and DA D2/D3 binding.

over 12 weeks of treatment, regardless of treatment condition (unpublished data). These results also add support to the notion that epigenetic changes may play a role in relapse. Directly targeting these epigenetic changes may be beneficial. Finally, it is important to note that we have also conducted a number of clinical trials with AUD patients and tobacco users over the last 10 years ([name] et al., 2006; Littlewood et al., 2014). Our demonstration of the importance of epigenetic regulation of reward related genes, and our success with clinical trials, provides evidence regarding feasibility of the proposed trial in terms of recruitment, data collection, and study completion.

### **Immune Function.**

While our program of research has focused more on epigenetic regulation, there is a substantial amount of data in the literature to suggest the importance of the LPS/TLR4 signaling cascade in the etiology and maintenance of AUDs (Mayfield et al., 2013). Based on this literature, we recently examined the association between cytokines and key alcohol phenotypes, including connectivity in the left and right executive control networks (LECN/RECN). Our previous work suggests that these two networks are important in the etiology of AUDs (Karoly, Weiland, Sabbineni, & [name], 2014). To generate effect sizes on the association between cytokines (TNF, IL-6, IL-8) and neural network connectivity, we assayed these markers in the plasma of 30 subjects in one of our existing datasets. The correlations with connectivity in the LECN and RECN ranged from  $r = -.24$  to  $r = -.55$  for TNF and IL-8. It is also important to note that the samples were not fresh, and the measures were not as sophisticated as the proposed approach that involves the collection of PBMCs. We now routinely collect PBMCs in one of our studies on aging and inflammation (PI: [name]) and we routinely utilize an assay that involves stimulating the PBMCs with LPS to examine the effects of LPS on inflammatory gene expression and cytokines. Given the superiority of these methods, we expect to see larger effect sizes in the proposed study.

---

## **IV. RESEARCH STUDY DESIGN**

---

### **Overview and Design of the Proposed Study.**

A 2 (Treatment: 8 weeks of MBRP vs. 8 weeks of RP)  $\times$  5 (Time: Baseline, 4, 8, 20, 32 weeks) mixed factorial design, where treatment is a between-subjects factor and time is a within-subjects factor, will be used to test the treatment outcome hypothesis in Aim 1. Subjects will be randomly assigned to receive MBRP or RP for a period of 8 weeks such that there are equal numbers of patients in each group. An intermediate assessment of the effects of treatment on immune system function and epigenetic regulation of dopamine genes will be collected at 4 weeks. Follow-up assessments will be obtained at 8 weeks (the end of treatment), 20 weeks (12 weeks after the end of treatment), and 32 weeks (24 weeks after the end of treatment).

#### ***Treatment:***

#### **Rationale for Treatment Conditions.**

MBRP was chosen as the experimental treatment because there is mounting evidence that MBIs have a significant effect on immune system function, including on targets that have been implicated in the maintenance of AUDs. To our knowledge, there are no other examples of psychosocial

interventions or pharmacotherapies that influence the immune system and epigenetics that are as well supported as MBRP. RP was chosen as the control condition in order to dismantle the effects of MBRP from RP, thereby isolating the effects of the mindfulness components. Our decisions regarding the overall length of treatment (8 weeks), length and content of individual sessions, subject selection, assessments, and follow-ups at 5 and 8 months after the end of treatment were based on recent trials of MBRP and RP ([name] et al., 2014; [name] et al., 2014).

### **MBRP and RP Implementation.**

Consistent with the treatment manuals and previously published papers, a goal of abstinence is encouraged but not required (see [name] et al., 2014). For scheduling logistics, we will not have a group format but instead each treatment will be provided individually. As noted in the budget justification, the consultants ([name] and [name]) along with [name] (Co-I), will be on-site at the inception of the study to provide feedback on the refinement and implementation of MBRP and RP. [name] and [name] will continue to provide expert supervision and consultation throughout the study. [name], who is widely known for her expertise with MBIs, will be onsite for supervision and training throughout the trial. Therapists will be selected from the graduate program in clinical psychology at the University of Colorado and will have a master's degree in clinical psychology and previous training in the fundamentals of psychological intervention provided by [name] or [name]. At the inception of the study, [name] will travel to Boulder to provide a two-day workshop on MBRP. At a separate time, [name] will travel to Boulder to provide a two-day workshop on RP. In advance of the training workshops, prospective therapists will study the relevant manual (MBRP or RP). The workshops will contain both didactic and role-play exercises. *Therapists will be cross-trained in the interventions and will lead an equal number of both conditions to prevent therapist effects.* After training, prospective therapists will be required to demonstrate competency in MBRP or RP by submitting audio recordings of pilot therapy sessions with patients recruited through the University of Colorado training clinic, who will not be part of the proposed study. The recordings will be reviewed by [name] and either [name] or [name] and rated using both the Yale Adherence and Competence Scale as well as the MBRP competence scale, using a 7-point Likert scale as described in previous reports ([name] et al., 2014). Therapists who demonstrate an average rating of 5 across the duration of the 8-week treatment will be certified to be a therapist for the trial. During the course of the trial, weekly supervision meetings will be convened and an on-site supervisor ([name] or [name]) will review at least one audio recording per week using the same rating scales to ensure consistency in the treatment throughout the duration of the trial. [name] will visit Boulder once per year to assess overall fidelity and progress of the trial. MBRP will consist of 8 weekly 1-hour sessions provided in an individual format, whereas RP will consist of the same format, time, location, and amount of assigned homework but will not contain the mindfulness content provided during MBRP.

Participants will be instructed to arrive at the CINC 10 minutes prior to their scheduled appointment and meet in Room 129. Participants will fill out a quick check-in survey on an iPad before their appointment begins in order to inform therapists of the extent to which they completed their home practice the week before. The check-in survey will also allow participants to record any questions they have for their therapist before the appointment begins. The room will have two chairs with a coffee table in between the chairs, along with meditation cushions. Water will be available in the room. At each session, the therapist will engage and guide the participant in a discussion and exercise. The session will last one hour.

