#### **Specific Aim 1 - Detecting Treatment Effects on Drinking Outcomes.**

The effect of the treatment on alcohol use outcomes (HYPOTHESIS 1) will be analyzed with a 2 (**Treatment:** 8 weeks of MBRP vs. 8 weeks of RP) x 5 (**Time:** Baseline, 4, 8, 20, 32 weeks) mixed general linear model with Heavy Drinking Days (HDD) as the primary outcome variable. We will also examine drinks per drinking day, ICS score, and liver function tests as dependent measures in each of 2 additional models, respectively. In the main analysis with HDD, a significant overall test of the treatment X time interaction will be followed by planned contrasts within the mixed model that allow us to test the superiority of MBRP over RP at the 8, 20, and 32 week follow-up points specifically. The FIML estimation procedure implemented in these analyses will allow us to utilize an “intent to treat” approach such that all subjects who are randomized will be included in the analyses (Schafer & Graham, 2002). It may be that the treatments are equally effective on drinking outcomes, and thus we will not see a direct effect of treatment on outcomes. Even in this case, it is possible that the mechanisms through which the treatments had their impact may differ. Thus, tests of Specific Aims 2 and 3 are still important and warranted.

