Subjects will then complete baseline questionnaires related to their demographics, history of drinking, smoking and drug use, and alcohol craving (measures listed below). Also, subjects will take six neurocognitive tests using the NIH toolbox application, which will assess their cognitive function in terms of memory and attention. If not eligible for the MRI, subjects will be randomly assigned to receive MBRP or RP for the next 8 weeks at the end of their baseline session and will also be given their microbiome sample collection kits at the end of the session. They will return the sample kits at their next scheduled session. Subjects will be compensated \$30 for completion of the baseline appointment.

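### Crossing therapists with arms guards against confounding by general therapist skill, but does not prevent therapist effects: no step secures the balance and the HDD model has no therapist term

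*Combined protocol and SAP*

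**What the plan says.** MBRP and RP Implementation sets individual therapy in both arms and states: "Therapists will be cross-trained in the interventions and will lead an equal number of both conditions to prevent therapist effects". Next, prospective therapists are "required to demonstrate competency in MBRP or RP by submitting audio recordings of pilot therapy sessions", and those who reach an average rating of 5 "will be certified to be a therapist for the trial". Recordings are rated on both the Yale scale and the MBRP competence scale. At least one recording a week is reviewed during the trial.

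On assignment, Overview and Design says that patients are "randomly assigned to receive MBRP or RP for a period of 8 weeks such that there are equal numbers of patients in each group". For patients who will have no scan, Baseline Session gives this timing: "subjects will be randomly assigned to receive MBRP or RP for the next 8 weeks at the end of their baseline session". Scanned patients learn their arm after the scan (MRI Scan I). The therapist appears next, at the Goal-setting Session; in the remote version the patient is introduced to the therapist there. No section says how a patient is given a therapist.

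On analysis, Specific Aim 1 is a treatment-by-time "mixed general linear model with Heavy Drinking Days (HDD) as the primary outcome variable". The Data Analysis Plan takes as covariates only variables on which the arms differ at pretest. From the Aim 1 power section to Secondary analyses there is no therapist factor, random effect, therapist-by-treatment test or clustering allowance. The number of therapists is not given.

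**The concern.** The trial sets out to separate mindfulness from relapse prevention while the same clinicians deliver both. Therapists can then matter in two ways. One may get better results in both arms (a difference in level), or may be better at one treatment than the other (therapist-by-treatment variation). Equal caseloads balance the first across arms. They leave the second untouched.

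Therapist-by-treatment variation can act only once therapy has started, so it falls on the treatment-by-time effect, which is the primary test. If it exists and the model omits it, the standard error is too small for a conclusion about MBRP in the hands of therapists generally. The balance that handles the first kind is promised, but no described procedure produces it.

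**Working it through.** **1. The plan's own figures.** Inputs from Power for Specific Aim 1: f = .10, 180 analysed (90 per arm), 5 time points, correlation .50, alpha .05. For the interaction, lambda = f² × N × m / (1 − r) = 0.01 × 180 × 5 / 0.5 = 18, on 4 and 712 degrees of freedom. Power is .942, which agrees with the plan's statement of well over .90. Attrition: 180 / 0.80 = 225, against about 226 stated. Both figures treat patients as independent, with no therapist component.

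**2. Formula.** With n patients per arm and k therapists, each with equal numbers in both arms, the variance of a two-arm contrast is multiplied by

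DE = (n/k) × s_TA + (1 − s_T − s_TA),

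where s_T is the share of HDD variance due to therapist level and s_TA the share due to therapist-by-arm. A test that ignores therapist has true alpha = 2 × (1 − Φ(1.96/√DE)). The values of k, s_T and s_TA are assumptions.

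**3. Therapists differ in level only (s_TA = 0).** DE = 1 − s_T.

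- s_T = .02: DE .98, alpha .048
- s_T = .05: DE .95, alpha .044
- s_T = .10: DE .90, alpha .039

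There is no inflation. Simulation (6,000 runs per setting; 4, 6 and 12 therapists) agrees, at .035 to .047. When the therapist is drawn at random regardless of arm, with no balancing, simulated alpha is .041 to .054.

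**4. Therapist-by-arm variation (s_T = 0).** DE = 1 + (n/k − 1) × s_TA, where n is half the total N.

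| k | Total N | n/k | DE at 2% | alpha | DE at 5% | alpha |
|---|---|---|---|---|---|---|
| 12 | 180 | 7.5 | 1.13 | .065 | 1.32 | .089 |
| 12 | 226 | 9.4 | 1.17 | .070 | 1.42 | .100 |
| 6 | 180 | 15.0 | 1.28 | .083 | 1.70 | .133 |
| 6 | 226 | 18.8 | 1.36 | .092 | 1.89 | .154 |

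Simulation check at k = 6, N = 180, with 5% therapist variance split equally between level and therapist-by-arm: DE = 15 × .025 + .95 = 1.325, so alpha is .089 by formula and .086 simulated.

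**5. Power.** Dividing lambda by DE at N = 180, a test that allowed for this variation would have power of about .91 (12 therapists, 2%) down to .74 (6 therapists, 5%), against .942. This is approximate: DE is derived for one two-arm contrast and carried over to the four-degree-of-freedom interaction.

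**The case against.** The strongest reply is that the design already does what crossing is meant to do. Balanced caseloads remove confounding of arm with general skill, and step 3 shows that omitting therapist is then mildly conservative. This stands, so the plan's claim is too strong rather than empty.

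Three stronger readings are tempting, and the documents do not support them.

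- **Certification covers only one treatment.** The competency sentence names the two treatments as alternatives, but it follows the statement that therapists are cross-trained and lead both conditions. Certification is for the trial, and both rating scales are used. The wording is ambiguous; it does not establish single-treatment certification.
- **Assignment ignores the therapist, or therapists are matched to patients by arm.** The text is silent on allocation. It commits to equal numbers and omits the mechanism. Choosing the therapist after the arm is known permits matching, but equally permits deliberate balancing.
- **Uneven caseloads by themselves inflate alpha.** Without blocking, a therapist with 28 patients has a probability of .345 of a split of 17:11 or worse. That shows only that equality is not secured; step 3 shows that chance imbalance leaves alpha near .05.

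The plan also has safeguards against mindfulness content entering RP sessions: weekly review of recordings on both scales, a mindfulness questionnaire as a manipulation check, a weekly practice questionnaire, and a planned analysis of mindfulness uptake. What is missing is sampling of recordings by arm.

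Finally, a therapist-by-treatment random effect is costly as a primary model. With 6 therapists the arm test has 5 degrees of freedom and a critical value of 2.57 instead of 1.96, about 31% larger, and the variance component is poorly estimated. This also stands, and places that model in a sensitivity analysis.

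**Conclusion.** The concern holds in a limited form. Equal crossing protects against confounding by general therapist skill and no more. No described step secures it, and no planned analysis includes therapist or examines therapist-by-treatment variation. True alpha for the planned test is about .039 to .048 if therapists differ only in level (2% to 10% of variance), and about .065 to .15 if 2% to 5% of HDD variance is therapist-by-arm with 6 to 12 therapists. The second range rests on assumed therapist numbers and variance shares, on a single two-arm contrast, and on treating the therapists as a sample from a wider group; for conclusions about these particular therapists alone it would not apply. The documents do not show that such variation exists, only that the plan could not detect it. This should be changed. The certification wording taken alone needs only clarification.

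**What to change.** **Analysis, possible at any stage before unblinding**

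- Record the treating therapist for every patient.
- Add therapist to the Aim 1 HDD model, as a factor or random intercept together with its change over time. The time part is needed because therapists can affect drinking only after baseline.
- Prespecify a sensitivity analysis that allows therapist-by-treatment variation, and report caseload and arm effect by therapist.
- Reword the claim to say that crossing guards against confounding of arm with general therapist skill.

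**Conduct, while enrolment is open**

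- Fix each patient's therapist from the schedule before the arm is revealed, and block the randomisation by therapist with concealed allocation. This delivers the equal numbers already promised.
- Reconcile the competency and manual wording with the cross-training statement, so that it is clear whether competency is shown in each treatment.
- Draw the recordings already reviewed from both arms.

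**Cost:** one variable the site already knows, SAP wording, a revised randomisation list and minor scheduling work. The sensitivity analysis will give a wider interval, noticeably so with few therapists because of the few degrees of freedom. For that reason it should accompany the primary analysis rather than replace it.
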